#### 4.11 Clinician-Chin Assessment Tool (C-CAT)

SMF ratings using the C-CAT will be conducted by the Investigator at screening and baseline and at study visits on Days 28, 56, and 84 to assess the change in SMF severity before and following treatment.

The C-CAT score will be based on the Investigator's clinical evaluation of the subject in the Frankfurt horizontal plane. Clinical evaluation will include palpation of the chin and neck area, anterior, oblique and profile views of the chin and neck, and observation of pronation, supination, and lateral movement of the head. The score will be determined using the rating scale definitions. The score will be recorded as a whole number. At screening, the score will be used in conjunction with inclusion criteria.

The C-CAT is defined below. The scale is A 5-point scale (scored 0-4).

The grading system categorizes 3 aspects of submental chin fat: bulge, (size of the submental fat bulge) neck (extension of the bulge into the neck, downward and lateral) and jawline (the appearance of the jawline, presence of fat and definition of the jawline).

Each grade contains a description and a line drawing. Each grade is distinct and non-overlapping.

#### Clinician Chin Assessment Tool (C-CAT)

Score	Line Drawing	Description
0		

No bulge under chin

No fat in the neck

No fat along the jawline; jawline is visible and well defined

1		

Barely visible bulge, only visible in lateral and oblique views, not visible in frontal view

No fat in the neck

No fat along the jawline; jawline is visible and well defined

2		

Small but visible bulge, visible from all angles (lateral, oblique and frontal)

No fat in the neck

Fat may be present in the jawline; jawline is still visible and defined

3		

Noticeable bulge; visible in all angles (lateral, oblique and frontal)

Fat extends downward into the neck but does not extend to the laryngeal prominence (mid-neck)

Fat may extend laterally along the jawline; jawline is visible but may be poorly defined

4		

Very noticeable bulge, visible in all angles (lateral, oblique and frontal)

Fat extends down the neck to the laryngeal prominence and may extend beyond

Fat extends laterally along the jawline; jawline is poorly defined and may be indistinguishable from the neck

A comprehensive training guide with representative photographic examples and line drawing to each grade will be provided to the study center sites for training and visual comparison. The clinician training materials are attached in Appendix C.

#### 4.12 Subject – Self-Chin Assessment Tool (S-CAT)

SMF ratings using the S-CAT will be conducted by the subject at screening and baseline and at study visits on Days 28, 56, and 84 to assess the change in SMF area following treatment.

The scale has 5 grades from 0 to 4. Each grade utilizing line-drawings and descriptors to identify 5 unique and non-overlapping grades.

The chin fat is categorized by the following features: bulge (size of the fat bulge) neck (extension of the bulge downward and laterally into the neck) and jawline (presence of fat and definition of the jawline).

Self Chin Assessment Tool (S-CAT)		
Score	Line Drawing	Description
0	  	

No bulge under chin

No fat in the neck

No fat along the jawline; jawline is visible and well defined

1	  	

Barely visible bulge, only visible from the side, not visible in the straight ahead view

No fat in the neck

No fat along the jawline; jawline is visible and well defined

2	  	

Small but visible bulge, visible from the front and sides views

No fat in the neck

Fat may be present in the jawline; jawline is still visible and defined

3	  	

Noticeable bulge; visible from the front and side views

Fat extends downward into the neck but does not extend to the Adam's Apple (mid neck)

Fat may extend laterally along the jawline; jawline is visible but may be poorly defined

4	  	

Very noticeable bulge, visible from the front and side views

Fat extends down the neck to the Adam's apple (mid-neck) and may extend beyond

Fat extends laterally along the jawline; jawline is poorly defined and may be indistinguishable from the neck

Self evaluations should be made sitting in an upright position with the chin at a right angle (as illustrated in the line drawings). Mirrors will be used to see the chin, neck and jawline from both front and side views.

A comprehensive training guide with representative photographic examples and line drawing to each grade will be provided to the subjects.

The subject self -assessment training material are attached in Appendix D.

#### **4.13 Subject's Satisfaction Questionnaire for SMF Appearance**

SMF satisfaction questionnaire will be conducted by the subjects at in screening visit and study visits on Days 28, 56, and 84 to assess the subject's satisfaction with their SMF after treatment. Subjects will be asked the following questions and will score their satisfaction based on the grades below:

How satisfied are you currently with the appearance of your chin, neck and jawline area?

Score	Grade
0	Extremely Satisfied
1	Satisfied
2	Somewhat satisfied
3	Neither Satisfied nor Dissatisfied
4	Somewhat Dissatisfied
5	Dissatisfied
6	Extremely Dissatisfied

How happy are you with the appearance of your neck as it relates to your chin fat?

Score	Grade
0	Extremely Satisfied
1	Satisfied
2	Somewhat satisfied

3	Neither Satisfied nor Dissatisfied
4	Somewhat Dissatisfied
5	Dissatisfied
6	Extremely Dissatisfied

How satisfied are you with the result of your treatment\*?

Score	Grade
0	Very dissatisfied
1	Dissatisfied
2	Somewhat dissatisfied
3	Somewhat satisfied
4	Satisfied
5	Very satisfied

How likely would you be to recommend this procedure to friends and family\*?

Score	Grade
0	Not at all likely
1	A little likely
2	Somewhat likely
3	Very likely
4	Extremely likely

\*subjects will be asked this question only at study visits on Days 28, 56, and 84

#### **4.14 Subject's Impact Questionnaires**

A set of questions will be asked to assess subject's impact based on their SMF appearance. This will be conducted by at screening and at study visits on Days 28, 56, and 84 to assess the change in SMF area following treatment.

A. How self-conscious are you about your appearance as it relates to your chin fat?

0-Not at all self-conscious  
1-A little self-conscious  
2-Moderately self-conscious  
3-Very self-conscious  
4-Extremely self-conscious

B. How bothered are you by the appearance of your chin fat?

0-Not at all bothered  
1-A little bothered  
2-Moderately bothered  
3-Very bothered  
4-Extremely bothered

C. How much do you think that the appearance of your chin fat effects your career or work life?

0-Not at all  
1-A little bit  
2- A moderate amount  
3-A great deal  
4-An extreme amount

D. How much does the appearance of your chin fat effect your relationships?

0-Not at all  
1-A little bit  
2-A Moderate amount  
3-A great deal  
4-An extreme amount

E. How much does the appearance of your chin fat effect your self-confidence?

- 0-Not at all
- 1-A little bit
- 2- A moderate amount
- 3-A great deal
- 4-An extreme amount

F. Do you feel self-conscious about the appearance of your chin fat when you look at photographs?

- 0-Not at all
- 1-A little bit
- 2- A moderate amount
- 3-A great deal
- 4-An extreme amount

G. Do you try to hide or camouflage your chin fat? For example, make-up and hair styles, beard hair, clothing or neck/head position?

- 0-Not at all
- 1-A little bit
- 2- A moderate amount
- 3-A great deal
- 4-An extreme amount

H. Do you feel self-conscious when you look at your chin fat in the mirror?

- 0-Not at all
- 1-A little bit
- 2- A moderate amount
- 3-A great deal
- 4-An extreme amount

I. How do you think the appearance of your neck effects your relationships?

- 0-Not at all
- 1-A little bit
- 2- A moderate amount
- 3-A great deal
- 4-An extreme amount

J. How heavy or thin do you think your chin fat makes you look?

- 0 - I look more than 10 pounds thinner than I am
- 1 - I look 10 pounds thinner
- 2 - I look 5 pounds thinner
- 3 - I look my weight
- 4 - I look 5 pounds heavier
- 5 - I look 10 pounds heavier
- 6 - I look more than 10 pounds heavier

#### **4.15 Physician Global Assessment Improvement Scale (GAIS) and physician assessment**

Investigators will assess the improvement in SMF following treatment by comparing the photographs of the subject taken at screening versus the photographs taken at study visits on Days 28, 56, and 84.

At each study visit, the Investigator will assess the improvement degree based on the following scale:

Global Aesthetic Improvement Scale (GAIS)		
Grade	Degree	Description
1	Very much improved	Optimal cosmetic result
2	Very improved	Marked improvement in appearance from the initial condition, but not completely optimal
3	Improved	Obvious improvement in appearance from the initial condition
4	No change	The appearance is essentially the same as the original condition
5	Worsened	The appearance is worse than the original condition

Clinicians will be asked which word best describes the amount of submental fat the subject has\*:

- No fat
- Barely visible pocket of fat
- Small but visible pocket of fat
- Visible pocket of fat amount
- Large pocket of fat

\*The question will be asked at screening and on study visits 28, 56 and 84 Days.

#### 4.16 Subject Global Assessment of Change and subject self-assessment

Subjects will be asked to self-assess their SMF appearance and change.

At each study visit, the subject will be asked to assess their improvement degree based on the following questions:

A. Looking in a mirror today, how would you rate the amount of your submental (under the chin) fat from 1 (not fat) to 10 (extreme fat) using the numerical rating scale? \*

1 2 3 4 5 6 7 8 9 10

No fat extreme fat

B. Subjects Global Self-Assessment of under the chin fat: Which word best describes the amount of your submental (under the chin) fat? \*

- No fat
- Barely visible pocket of fat
- Small but visible pocket of fat
- Visible pocket of fat amount
- Large pocket of fat

\* questions will be asked at screening visit and on Days 28,56 and 84

At each study visit (Day 28,56 and 84), the subject will be asked to assess their improvement degree based on the following scale:

Score	Grade
0	Extremely improved
1	Very much improved
2	Improved
3	No Change
4	Worse
5	Very much worsened
6	Extremely worsened

#### **4.17 Evaluation of Response**

Evaluation of response will be conducted on Days 28, 56, and 84 following injection of RZL-012 or placebo.

#### **4.18 Compliance Monitoring**

Compliance monitoring will include compliance assessment by site coordinator at the study visits, including but not limited to subject questioning.

### **5.0 SAFETY ASSESSMENTS**

#### **5.1 Collection of Adverse Events Data**

Data regarding treatment-emergent AEs (TEAEs) will be collected in this study. TEAEs are events that are not present at baseline, or if present at baseline, have worsened in severity. AEs will be assessed while the subjects are in the study. AEs assessed by the Investigator as related to study drug and “ongoing” at discharge will be monitored by the Investigator until resolved or until the subject is deemed “lost to follow-up”.

Any AEs reported by the subject or noted by the Investigator or his/her designee will be recorded on the eCRF regardless of the Investigator opinion of causality. The following information will be recorded for each AE: description of the event, date and time of onset, date and time of

resolution, severity, causal relationship to study drug, outcome, action taken with the study drug and any treatment given.

The AEs reported during the trial will be graded, documented, and assessed in regards to their clinical significance and relation to study drug. Treatment area evaluations including, but not limited to evaluation of edema, bruising, dysphasia, dysphonia, erythema, dyspigmentation, induration, numbness, pain, paresthesia, pruritus, skin ulceration and necrosis, injury to the marginal mandibular nerve, vascular and nerve injury and tissue damage to nearby vulnerable anatomic structures..

All abnormal changes from baseline will be collected, graded with regards to severity or clinical significance, assessed for causal relationship and recorded on the eCRF.

## **5.2 Complete or Targeted Physical Examination**

The Investigator will perform a complete PE at screening and on Day 84 visit.

## **5.3 Vital Signs**

Vital signs (systolic and diastolic sitting position blood pressure, pulse rate, respiratory rate, and body oral temperature) are to be obtained at screening to ensure compliance.

Additional vital sign measurements to assess subject's safety will be performed at baseline (Day 0) prior to treatment and after treatment, Day 1, and during study visits on Days 7, 28, and 56.

## **6.0 PHARMACOKINETICS**

No PK measures will be assessed during this study.

## **7.0 EFFICACY**

Efficacy measures include the following:

- Efficacy of RZL-012 versus placebo on SMF reduction measured on Day 84 versus baseline using the C-CAT.
- Assessment of the reduction in SMF on Day 84 as compared to baseline using the caliper measured submental thickness, MRI measured SMF volume, and the S-CAT.
- Assessment of SMF improvement using the Physician global SMF assessment, GAIS, Subject Global Assessment of Change Scale, Subject Global Self-Assessment and subject satisfaction questionnaire, subject's impact questionnaire.

## **8.0 STUDY VISITS AND PROCEDURES**

Refer to [Appendix A](#) for the Schedule of Study Procedures.

## 8.1 Screening (Days -28 to -1)

The Investigator or his/her approved designee must explain the nature of the study protocol and associated risks to the potential study participant. The potential participant must be allowed to review the study information and to ask questions before being asked to sign the Informed Consent Form (ICF). Written informed consent must be provided by the potential study participant prior to initiation of any screening evaluations or other study-related procedures. The signature date and the name of the individual at the site who obtained the informed consent will be recorded in the subject's medical record.

After written informed consent is obtained, the subject will be assigned a screening number and will undergo the designated screening procedures listed in Appendix A. The Investigator, sub-investigator or delegate will assess the results of these screening evaluations to determine eligibility for entry into the study according to the inclusion/exclusion criteria listed in [Section 3.0](#).

Screening evaluations may be performed up to 28 days in advance of dosing but must be completed at least 1 day prior to Day 0.

The following study evaluations and procedures are required to determine eligibility at pre-screening visit:

- C-CAT
- S-CAT
- 2D photography

The following study evaluations and procedures are required to determine eligibility in the second part of the screening visit:

- Obtain and record a medical history, including demographics, prior medications, and concomitant medications.
- Complete physical examination
- Vital signs
- ECG
- Height and weight measurements
- Blood and serum samples for the following laboratory evaluations:
  - Hematology
  - Serum chemistry
  - Coagulation

- Pregnancy (if applicable)
- Caliper measurement of SMF thickness
- MRI
- Physicians Global Assessment Question
- Subject's satisfaction questionnaire (appearance of submental area)
- Subject Global Assessment questions
- Subject's impact questionnaire

Subjects may be re-screened if they were screened and not dosed within 28 days. The following procedures will be performed: vital signs and weight measurements.

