**Figure 3: Injection Sites for Phase 2A Study**

#### RZL-012-P2aUS-001.4 Study Results:

In this study, in which significantly higher doses were tested (up to 180 mg), RZL-012 was found to be safe in all cohorts. There were no clinically significant changes in vital signs, ECG and all blood laboratory parameter. The most commonly reported AEs for which there seemed to be a causal relationship to active treatment, due to the higher incidence in the active treatment groups compared to the placebo groups, were injection site pain and injection site edema. Most AEs were transient. There was only a single case in the highest injected dose, Cohort 4, where erythema and edema were still observed up to Day 140.

The only systemic effect due to the subcutaneous injection of RZL-012 was elevation in d-dimer values at the highest injected dose of 180 mg. However, this increase was transient, up to 3 days after injection, and non-clinically significant. Further review of coagulation parameters revealed there was no clinically significant activation of the coagulation system nor any presence of Disseminated Intravascular Coagulation (DIC). The absence of any clinical symptoms related to elevation of D-dimer supports a direct link between RZL-012 induced inflammation and elevated D-dimer levels, unrelated to venous thromboembolic disease.

Biopsies taken from two injection sites revealed no damage to the skin 56 days following RZL-012 injection. Based on the histology results, the process that seemed to be dominant is fat necrosis and infiltration of macrophages into the necrotic fat tissue that resulted in a replacement of the local fat tissue by fibrotic tissue.

A decrease from baseline in SFM ratio (injected/non-injected side), as assessed by MRI, was noted in RZL-012 treated subjects of Cohorts 2 – 4 at all study time points. In addition, a dose dependent response was evident and statistically significant differences in SFM were found in RZL-012 treatment groups versus placebo. Among Cohorts 4 subjects who were monitored until 168 days post injection, a clear reduction in SFM was noticed (-14.32%). Cohort 4 subjects demonstrated the largest reduction in SFM at Day 56 (-18.10%).

There were no major changes over time and no specific trend to suggest a dose correlation response in any of the parameters of lipid profile (TC, TG, LDL, HDL, and FFA) and fasting glucose.

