### 3.2 Exclusion Criteria

Subjects must **NOT** meet any of the following Exclusion criteria to be eligible for enrollment:

1. Is unable to tolerate subcutaneous injections.
2. Has dysfunctional gallbladder activity (e.g., underwent cholecystectomy or cholecystitis).

3. Has any uncontrolled systemic disease that is not stabilized (i.e., cardiovascular disease, mental illness).
4. Has had treatment with botulinum toxin injections in the neck or chin area within nine (9) months prior to screening.
5. Has used anticoagulation therapies that may increase bleeding or bruising (i.e., aspirin, ibuprofen, vitamins, and herbal preparations) for seven (7) days prior to treatment.
6. Has skin laxity (i.e., elastosis, skin crepiness, skin redundancy, skin draping, vertical and/or horizontal skin bands and folds, blunting of cervical mental angle, loss of opposition of skin to underlying neck structures due to skin laxity) that could obscure the evaluation and treatment of SMF.
7. Has any scars, unshaven hair, tattoos, facial hair or jewelry on or near the proposed treatment area.
8. Has presence of structures or confounding factors that may interfere with assessing SMF such as but not limited to enlarged submandibular salivary and/or parotid glands, micrognathia, chin implant, soft tissue volume augmentation of chin and/or jawline, pronounced platysmal bands and deep necklace lines or presence of facial jowls that could obscure the evaluation of SMF.
9. Has a fat bulge under the chin that is too large to be adequately treated by 32+/-4 contiguous injections on a 1cm grid .
10. Has a fat bulge under the chin that is of an insufficient volume to allow 28 injections within a contiguous 1 cm grid.
11. Has significant history or current evidence of a medical, psychological or other disorder that, in the Investigator's opinion, would preclude enrollment in the study.
12. Has an active dermatitis or open wound in the proposed treatment area.
13. Has abnormal coagulation tests (PT, PTT)
14. Has D-dimer value >0.64mg/L in screening visit
15. Has an active bacterial, fungal, or viral infection in the proposed treatment area.
16. Has a pre-existing skin condition in the submental region that, at the Investigator's discretion, may confound evaluation or analysis.

17. Has previously had treatments or surgery in the submentum, such as but not limited to, focused ultrasound, radiofrequency, cryolipolysis, liposuction, sodium deoxycholate, or neck lift.

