#### **4.4 Vital Signs**

Vital signs (systolic and diastolic sitting position blood pressure, pulse rate, respiratory rate, and body oral temperature) are to be obtained at screening to ensure compliance.

Additional vital sign measurements to assess subject's safety will be performed at baseline (Day 0) prior to treatment and after treatment, Day 1, and during study visits on Days 7, 28, and 56.

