#### **4.6 Height and Weight**

Height will be reported in centimeters at screening. Body weight will be reported in kilograms (kg) at screening.

Weight measurement will be performed at screening to determine the BMI value. An additional weight measurement will be performed at baseline and at study visits on Days 56 and 84 to verify no significant changes in weight throughout the assessment of SMF changes during the study.

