#### **4.7 Clinical Laboratory Evaluations – Hematology and Serum Chemistry**

Screening blood samples and urine specimens for laboratory evaluation will be collected at screening to confirm eligibility. Additional blood samples will be collected at Day 1, 7, 28 and Day 84 study visits for an assessment of hematology and serum chemistry.

If there are clinically significant alerts obtained at any visit, an unscheduled visit will be added for additional blood sampling.

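### The re-screening rule in Protocol 8.1 conflicts with the protocol's own 28-day limit: as written, D-dimer, coagulation, laboratory and caliper values can be out of date at dosing

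*Protocol*

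**What the plan says.** Protocol 8.1 sets the general rule: "Screening evaluations may be performed up to 28 days in advance of dosing". It then lets a subject who was screened but not dosed within 28 days be re-screened, and lists what is done: "The following procedures will be performed: vital signs and weight measurements".

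Both items already take place on Day 0 for every subject. Section 4.4 says "Additional vital sign measurements to assess subject's safety will be performed at baseline (Day 0) prior to treatment", and section 4.6 says "An additional weight measurement will be performed at baseline and at study visits on Days 56 and 84". The Day 0 list in 8.2 also has confirmation of eligibility, concomitant medications, a urine pregnancy test where applicable, S-CAT and C-CAT.

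Blood is taken at screening, after which section 4.7 says "Additional blood samples will be collected at Day 1, 7, 28 and Day 84 study visits". The caliper is read at screening and then on Days 28, 56 and 84 (section 4.8). Appendix A and the SAP schedule agree with both.

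Two exclusions depend on the blood results. Exclusion 13 concerns coagulation: section 3.2 names PT and PTT, and the synopsis names aPTT, INR and PT against the upper limit of normal. Exclusion 14 reads "Has D-dimer value >0.64mg/L in screening visit". SAP section 6 takes the last evaluable value before injection as baseline and gives no maximum age.

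**The concern.** Re-screening applies only to subjects who have passed the 28-day limit. These are the subjects whose results may have expired, yet the two procedures listed for them are ones they would have on Day 0 anyway. A site that follows the sentence literally renews nothing that has lapsed.

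The main stake is the check before dosing. The coagulation exclusion carries no date, so an old normal result can satisfy it. The D-dimer exclusion is tied to the screening visit, so a later rise is neither measured nor disqualifying as written. The treatment is a single session of up to 270 mg that cannot be withdrawn once given. The next blood sample, on Day 1, can detect a problem but cannot prevent exposure.

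The lesser stake is the reference for change: laboratory change from baseline in the safety summaries, and caliper change as a secondary endpoint.

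**Working it through.** The plan figure at issue is the 28-day limit. It is a rule, so there is nothing to recompute, and the check is a trace through the schedule.

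**Which measurements are renewed before dosing in a re-screened subject**

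| Measurement | Re-screening (8.1) | Day 0 before injection (8.2, 8.4) | Next scheduled |
|---|---|---|---|
| Vital signs | yes | yes | Day 0 post-dose |
| Weight | yes | yes | Day 56 |
| C-CAT, S-CAT | not listed | yes | Day 28 |
| D-dimer, PT, PTT, INR (hematology panel, 4.7.1) | not listed | no | Day 1 |
| Serum chemistry | not listed | no | Day 1 |
| Caliper | not listed | no | Day 28 |
| ECG | not listed | no | Day 7 |
| MRI | not listed | no | Day 84 |

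The list adds no type of measurement beyond Day 0.

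**How old the results can be.** Re-screening starts after 28 days. If the re-screening visit opened a second 28-day window (an assumption), a carried-over result could be more than 28 + 28 = 56 days old at dosing. Screening has two visits and blood is drawn at the second, so the results *can* be over 28 days old but need not be in every case.

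**Size of the caliper effect.** The documents give no SD for caliper change and no re-screening rate, so both inputs below are assumptions.

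- f = fraction of subjects with an out-of-date baseline, taken as 5% to 20%.
- r = SD of the extra drift divided by the SD of change, taken as 0.25 to 0.5.
- SD ratio = √(1 + f·r²). Effective n per group = 45 / (1 + f·r²), with 45 from Protocol 12.1.
- Power: two-sample t-test, two-sided alpha 0.05, 45 per group, standardized difference 0.691, which gives 90% power with current baselines. The 90% is a reference point only; Protocol 12.1 states power for the C-CAT endpoint alone.

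| f | r | 1 + f·r² | SD ratio | Effective n | Power |
|---|---|---|---|---|---|
| 0.05 | 0.25 | 1.0031 | 1.0016 | 44.9 | 0.899 |
| 0.10 | 0.50 | 1.0250 | 1.0124 | 43.9 | 0.893 |
| 0.20 | 0.50 | 1.0500 | 1.0247 | 42.9 | 0.886 |

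The SD rises by 0.2% to 2.5%, which equals losing 0.1 to 2.1 of 45 subjects per group. With 41 per group and a standardized difference of 0.725, the powers are the same to three decimals.

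**Direction.** The baseline ages before randomization, so the ageing cannot depend on the assigned arm. It adds noise to the comparisons between arms but does not bias them.

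**The case against.** The strongest reply is that the sentence does not waive the 28-day rule. The rule stands a few lines above it, section 2.2 repeats it, and the Appendix A screening column (Day -28 to Day -1) includes the laboratory tests and the caliper. One can argue that listing two procedures alone would be pointless if everything had to be repeated. But the two are also redundant with Day 0, so redundancy does not settle the meaning. This part stands: what can be shown is a conflict inside 8.1. A reader might infer that results of unlimited age are permitted, but that follows only if the general rule is taken as waived, and the protocol does not say so.

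There are also partial safeguards:

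- Concomitant medications are reviewed on Day 0. Exclusions 5 and 26 cover recent drugs that promote bleeding or bruising and chronic NSAIDs, so one clear route to newly abnormal coagulation is checked.
- A history of coagulopathy or of venous thrombosis is excluded separately.
- The weight checks give the caliper baseline some protection.
- Confirming eligibility on Day 0 may prompt a site to repeat the tests, though nothing requires it.

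The clinical signal is mild. D-dimer rose at 180 mg in the Phase 2a study in overweight and obese subjects, but the protocol says "However, this increase was transient, up to 3 days after injection, and non-clinically significant". That study reports no clinically significant change in blood laboratory parameters otherwise. The Phase 0 ALT rise was one subject, found 17 days after injection, and transient. No chemistry value is an eligibility criterion, so old chemistry cannot admit a subject against a stated laboratory limit. Its case is only that of a current reference value.

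A reader might also infer that MRI is exempt because Appendix A, footnote f, places it after the subject qualifies. That fixes its order, not its age at dosing; the SAP's 10-day window from the clinic visit does not say what happens at re-screening either. MRI has the same gap. So does the ECG, which the SAP lists beside the laboratory tests for change from baseline.

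**Conclusion.** The point holds as an internal conflict in Protocol 8.1. Followed literally, the re-screening sentence lets D-dimer and coagulation results older than 28 days satisfy exclusions 13 and 14, and lets laboratory and caliper baselines be equally old. It is a minor point that is cheap to correct.

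Its reach depends on how many subjects are re-screened, which the documents do not give and which may be zero. It does not touch the primary endpoint or the C-CAT/S-CAT responder endpoints, because both scales are rated on Day 0. For the caliper, the loss under the assumed range is at most about 1.4 percentage points from 90% power (90.0 − 88.6). A reader who inferred a threat to the efficacy conclusions would find no support for it. The case rests on the eligibility check and on consistency.

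**What to change.** Replace the re-screening sentence in 8.1 with:

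> Vital signs and weight will be repeated. Hematology (including D-dimer, PT, PTT and INR) will also be repeated if the earlier result will be more than 28 days old at dosing, and the D-dimer and coagulation exclusions apply to the repeat result.

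Serum chemistry can be run on the same draw and the caliper read at the same visit, which keeps the change-from-baseline references current. Whether to repeat the MRI is for the sponsor to decide in view of cost. The text should not imply that MRI or ECG is exempt.

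The cost is one blood draw, the wait for its result before dosing and a short caliper reading, in re-screened subjects only. All are tests the protocol already performs.
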